5.2.2. Estimand

Population: subjects undergoing primary unilateral elective TKR surgery

Endpoint: Total VTE

Measure of Intervention: the effect of the initially randomized treatment that would have been observed had all subjects remained on their treatment throughout the DB dosing phase.

5.2.3. Analysis Methods

a) In support of the dose escalation decision within Part 1, the following will be summarized.

- The number of subjects with Total VTE, and the secondary endpoint Major VTE (see section 5.3.1 for definition) up to Day 10-14 visit observation period and the corresponding lower bound of 1-sided 90% confidence interval for dose escalation by cohort/dose. If the computed lower bound based on any or both observed Total VTE, Major VTE rates, in the highest JNJ-64179375 dose studied, is greater than a predefined threshold then it could signal that further dose escalation be considered if there is no safety issue at the dose considered.

The lower bound of 1-sided 90% confidence interval used for comparison to the threshold is a one sample CI, which is equivalent to a lower bound of 2-sided 80% CI., that can be obtained using the Exact method in PROC FREQ (in SAS).

Note that the suggested guidelines in Table 2 in section 3.1.1 provide similar information in terms of number of Major VTE events for the thresholds 2%, 3% or 4%.

- The number of subjects with Total VTE, Major VTE up to Day 10-14 visit observation period and the corresponding lower bound of 1-sided 90% confidence interval for the between JNJ-64179375 dose and apixaban (or cumulative apixaban beginning from cohort 1) treatment difference of event rate for dose escalation by cohort/dose.

The lower bound of 1-sided 90% confidence interval used for comparison to the threshold (0) is a two sample CI will be based on Miettinen and Nurminen (1985) method and will be computed in SAS following the closed form formulas for the method (Garner W). This method, unlike the most widely known Wald method (ie, normal approximation), does not produce undesirable results in extreme cases (eg, when the proportions are near 0 or 1).

Summaries from the above, will be presented as side by side for CEC adjudicated, investigator reported and best available Total VTE, Major VTE events, where best available is always CEC adjudicated if a subject has both CEC adjudicated and investigator reported events.

- Continual Reassessment Method (CRM), a model based approach commonly used in oncology dose escalation study to determine MTD, will also be employed to predict event rates in next higher dose to guide the dose escalation process.

b) For the unblinded data review planned after all subjects are expected to have completed the Day 10-14 visit for Part 1, the following summary and analysis will be performed.

- Incidence of total VTE, major VTE with associated component events up to day 10-14 visit observation period will be summarized by treatment group for the modified ITT (mITT) analysis set. 90% confidence intervals for the odd ratio of each JNJ-64179375

dose over apixaban event rate with respect to Total VTE and Major VTE events will also be constructed.

- Dose response of JNJ-64179375 with respect to total VTE will be assessed using a two-stage generalized least squares approach model fitting methodology (Pinheiro et al, Stat in Med, 2013). That is, in the first stage, ANOVA-type model to the binary, total VTE data, based on the logistic regression model are fit using dose as factor. In the second stage, various candidate models (on logit scale) are fit using the estimates (from first stage) employing the Multiple Comparisons and Modeling (MCPMod) approach to the dose levels and associated variance-covariance matrix estimates from stage 1. The following candidate models will be considered: linear, emax, exponential, logistic and sigEmax. Dose-response effect are tested using a model-based multiple contrast test to select one (or several) model(s) from the significant shapes. The best fitting model to the data are picked using either the gAIC or aveAIC model selection criterion. The model with the smallest gAIC or aveAIC value is considered to fit the data best. Plots of the observed data and model fit including the 95% confidence intervals of the fitted lines will be presented using response rate on the y-axis and dose on the x-axis

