9.2.1. Assessments for DVT

Unilateral Venography

Venography assessments of the operated leg will be performed by injecting contrast agent into a foot vein and obtaining x-ray images of the proximal and distal leg veins consistent with the technique described by Rabinov and Paulin.²⁶ Evaluable venography assessments require the visualization of all of the deep veins except for the muscular, anterior tibial, and deep femoral veins. A diagnosis of DVT will be made if a constant intraluminal filling defect is observed in at least 2 images. An ultrasound will be performed in those subjects with suspected symptomatic DVT prior to the Day 10-14 visit. In these cases, if the ultrasound confirms symptomatic proximal DVT, a subsequent venography assessment is not required. If the ultrasound is negative or confirms a distal DVT, the venography assessment should be conducted on the Day 10-14 visit. Details regarding the timing of the venography assessment are provided in Section 9.1.3, Double-Blind Dosing Phase.

Study-specific venography assessment training will be provided to each study site. Each study site will be responsible for identifying at least 1 primary person to perform the venography assessments for subjects. Evaluability of the venography assessments based on centrally adjudicated data will be monitored for each site on an ongoing basis. If venography assessment performance is considered not acceptable, then further randomization by the investigator may be suspended until additional training or retraining is provided. Additional details regarding the venography procedure and study-specific training requirements will be provided in a venography manual, which will be provided separately to the study sites.

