11.2. Sample Size Determination

A total of 1,500 subjects are planned for this study, of which up to 300 subjects will be enrolled in Part 1 and the remainder for the entire study will be enrolled in Part 2. In Part 1, the sample

NCT03251482 Clinical Protocol 64179375THR2001 Amendment 1

size is not based on hypothesis testing but rather on making a preliminary assessment of the bleeding risk for the doses of JNJ-64179375. The event rate of any bleeding up to 14 days for apixaban 2.5 mg twice daily is expected to be between 5% and 10%. Figure 2 shows the probability to flag a higher event rate compared to apixaban for any dose of JNJ-64179375 in Part 1, assuming that the true underlying bleeding event rate in the apixaban group is 5%, 7.5%, or 10%. The figure presents the numbers of subjects in the JNJ-64179375 and apixaban treatment groups in rows and columns, respectively. The assumed event rate in the JNJ-64179375 group is presented as the relative risk to apixaban in the horizontal axis; the statistical comparison is based on the difference between event rates.

When the true underlying event rate in the apixaban group is 7.5%, there is a 67% probability for a dose of JNJ-64179375 to have the lower bound of the 1-sided 90% CI for between-treatment difference exclude 0 if the true relative risk (or risk ratio) is 3 (ie, the true underlying event rate in the JNJ-64179375 group is 22.5%), with 40 subjects in the JNJ-64179375 group (ie, any 1 planned cohort of JNJ-64179375 subjects) and 30 subjects in the apixaban group (ie, pooled apixaban subjects from 3 planned cohorts). The probability will increase to 81% when the dose of JNJ-64179375 is repeated in another planned or optional cohort, where there will be 80 subjects in the JNJ-64179375 treatment group and 40 subjects in the pooled apixaban group.

Figure 2:Probability to Flag a Higher Event Rate in the JNJ-64179375 Group Than in the Apixaban
Group at a 1-Sided, 10% α-Level

In Part 2, it is anticipated that 10% to 20% of subjects will either not have the venography assessment of the operated leg performed as scheduled or will not have an evaluable venography assessment for any DVT or proximal DVT. Assuming that 80% of venography assessments are

NCT03251482

Clinical Protocol 64179375THR2001 Amendment 1

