Following primary unilateral elective TKR surgery, eligible subjects in Part 1 will be randomly assigned to a single-ascending IV dose of JNJ-64179375 or apixaban 2.5 mg given orally twice daily for 10 to 14 days. Six cohorts of up to approximately 50 unique subjects per cohort (total of up to approximately 300 unique subjects) are planned but the number of cohorts and the size of each cohort may be adjusted based on the ongoing unblinded data review by the Operations Committee (OC). Within each cohort, subjects will be randomized in a 4:1 ratio to JNJ-64179375 or apixaban, respectively (ie, approximately 40 subjects to JNJ-64179375: approximately 10 subjects to apixaban). JNJ-64179375 will be administered in a dose-escalation manner, with planned doses of 0.3, 0.6, and 1.2 mg/kg in Cohorts 1, 2, and 3, respectively. In Part 1, the OC will be responsible for reviewing ongoing safety and efficacy data by unblinded subject treatment assignments approximately every 1 to 3 weeks. Subjects enrolled in the optional cohorts will receive doses of JNJ-64179375 in the range of 0.1 to 1.8 mg/kg, which will be dependent on the available preliminary safety, tolerability, efficacy, PK, and PD data obtained from the preceding cohorts (refer to Section 6, Dosage and Administration for additional details). After all the subjects in Part 1 are expected to have completed the Day10-14 visit, an unblinded data review will be conducted by the OC, Steering Committee (SC), Independent Data Monitoring Committee (IDMC), and sponsor to determine the dose range and doses for Part 2. A schematic diagram of the study design (Part 1) is provided in [Figure 1](#) below.

Figure 1: Schematic Overview of Part 1 of the Study

‡ Double-dummy design: Subjects in both parts will receive a single dose of IV JNJ-64179375 or JNJ-64179375 placebo and 10 to 14 days of apixaban or apixaban placebo PO BID, followed by unilateral venography and follow-up study visits through Week 18. Unique subjects will be enrolled in each part and within each part unique subjects will be enrolled in each cohort.

† Six cohorts of up to approximately 50 unique subjects per cohort (total of up to approximately 300 unique subjects) are planned but the number of cohorts and the size of each cohort may be adjusted based on the ongoing unblinded data review by the Operations Committee.

BID = twice daily; IV = intravenous; PO = by mouth

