2.4.3.1. Primary Efficacy Analysis Set

Modified Intent to Treat (mITT) analysis set includes all randomized subjects with an evaluable venography assessment or a confirmed symptomatic VTE event, or any death.

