5.3.1. Definition

Major VTE is defined as the composite of proximal DVT (asymptomatic confirmed by venography assessment of the operated leg or objectively confirmed symptomatic), nonfatal PE, or any death

→ Major VTE = Proximal DVT (Asymptomatic or Symptomatic) + Nonfatal PE + Any death

The following maps the locations in eCRF of the investigator reported components needed in the definition of Major VTE:

Major VTE Component	eCRF Form name(s)	Comments
Symptomatic DVT (Proximal)	Suspected Symptomatic Deep Vein Thrombosis	In the opinion of the investigator, does this event meet the protocol definition of Symptomatic Deep Vein Thrombosis? → YES & Proximal
Asymptomatic DVT (Proximal)	Planned Day 10-14 Venography	Proximal clot
Nonfatal PE	Suspected Symptomatic Pulmonary Embolism & Death	Suspected symptomatic PE & Alive
Death	Death	

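### Major VTE is analysed on a set that requires readable distal veins it does not use, so proximal-readable subjects, and possibly an asymptomatic proximal DVT on an incomplete film, fall outside the analysis

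*SAP*

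**What the plan says.** SAP 5.2.3(b), the review at the end of Part 1, covers total and major VTE in one sentence: "Incidence of total VTE, major VTE with associated component events up to day 10-14 visit observation period". That sentence names mITT as the one set for both endpoints. The odds-ratio intervals against apixaban for both endpoints are in the same item.

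SAP 2.4.3.1 defines mITT as "all randomized subjects with an evaluable venography assessment or a confirmed symptomatic VTE event, or any death". There is no second version of the set for major VTE.

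Protocol 9.2.1 defines the film standard: "Evaluable venography assessments require the visualization of all of the deep veins except for the muscular, anterior tibial, and deep femoral veins". Three vein groups are exempt; the other distal veins must be seen. The same section gives the diagnostic rule, which sets no completeness condition: "A diagnosis of DVT will be made if a constant intraluminal filling defect is observed in at least 2 images".

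SAP 5.3.1 defines the endpoint: "Major VTE = Proximal DVT (Asymptomatic or Symptomatic) + Nonfatal PE + Any death". Its eCRF map takes an asymptomatic event from a proximal clot on the planned venogram, again without an evaluability condition.

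Protocol 11.2, writing about Part 2, expects 10% to 20% of subjects to have no scheduled venogram or a film that "will not have an evaluable venography assessment for any DVT or proximal DVT". That wording recognises two kinds of evaluability. The SAP carries only one.

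**The concern.** The admission rule and the endpoint do not match. A film with clear proximal veins and one unreadable, non-exempt calf vein answers the asymptomatic DVT question for major VTE, yet the subject is excluded.

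Two consequences follow. First, precision is lost on an uncommon key secondary endpoint, in arms that are already small: each Part 1 cohort is planned as "approximately 40 subjects to JNJ-64179375: approximately 10 subjects to apixaban". Second, an event may be lost. The mITT exceptions for subjects without an evaluable film cover symptomatic VTE and death only. A subject with an asymptomatic proximal DVT on an incomplete film meets the diagnostic rule but not the entry rule. If such subjects are dropped, the major VTE rate is biased downwards.

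**Working it through.** **Inputs.** Protocol Table 5 gives n/N for total and major VTE in ADVANCE-1 and ADVANCE-2. The symptomatic-VTE row supplies the larger base of 1599, 1596, 1528 and 1529 subjects.

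**Reproducing the plan's figures (apixaban arms).** ADVANCE-1: 104/1157 = 9.0% and 26/1269 = 2.0%. ADVANCE-2: 147/976 = 15.1% (printed as 15.0) and 13/1195 = 1.09%. These agree with Table 5 to rounding.

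**Comparing denominators.** Let T be the total VTE denominator and M the major VTE denominator. The share of usable subjects lost by using T is 1 - T/M. The gain from moving from T to M is M/T - 1. These have different bases and should not be interchanged.

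| Arm | T | M | M - T | Lost, 1 - T/M | Gain, M/T - 1 |
|---|---|---|---|---|---|
| ADVANCE-1 apixaban | 1157 | 1269 | 112 | 8.8% | 9.7% |
| ADVANCE-1 enoxaparin | 1130 | 1216 | 86 | 7.1% | 7.6% |
| ADVANCE-2 apixaban | 976 | 1195 | 219 | 18.3% | 22.4% |
| ADVANCE-2 enoxaparin | 997 | 1199 | 202 | 16.8% | 20.3% |
| Four arms pooled | 4260 | 4879 | 619 | 12.7% | 14.5% |

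**Carried to a Part 1 dose arm of 40 (assumption).** Dividing T and M by the symptomatic-row base and multiplying by 40:
- mITT: 40 × 1157/1599 = 28.9; 40 × 1130/1596 = 28.3; 40 × 976/1528 = 25.5; 40 × 997/1529 = 26.1.
- Proximal-evaluable set: 40 × 1269/1599 = 31.7; 40 × 1216/1596 = 30.5; 40 × 1195/1528 = 31.3; 40 × 1199/1529 = 31.4.

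The difference is about 2 to 6 subjects per dose.

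**Bound from the protocol's own expectation.** If 80% of the 40 are evaluable, mITT holds 32 and at most 8 more can be usable: a loss of at most 8/40 = 20% and a gain of at most 8/32 = 25%. At 90% (36 subjects) the limits are 4/40 = 10% and 4/36 = 11%.

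**Illustration with SAP Table 2.** Exact one-sided 90% lower bounds are 2/26 = 2.06%, 2/29 = 1.85% and 2/32 = 1.67%. Two events cross the 2% reference with 26 subjects but not with 29 or 32, in line with Table 2, which stops at 26. If the excluded subject carries an event, the direction reverses: 2/28 = 1.92% crosses nothing, while 3/32 = 3.49% crosses 2% and 3%.

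**The lost event, by text.** The diagnosis needs a filling defect in two images (Protocol 9.2.1). The eCRF map needs a proximal clot (SAP 5.3.1). Entry to mITT needs an evaluable film, confirmed symptomatic VTE or death (SAP 2.4.3.1). An asymptomatic proximal DVT on an incomplete film satisfies the first two and fails the third.

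**The case against.** **The size is borrowed.** The documents do not say why the Table 5 denominators differ; attributing the gap to films readable only proximally is an inference. Those studies included subjects with one or both knees replaced, and ADVANCE-2 counted VTE-related death rather than any death in major VTE. This trial uses unilateral films, site training and continuing checks of evaluability. All of this stands, so the percentages are conditional.

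**Table 2.** A reader might infer that the mITT rule decides whether an escalation threshold is crossed. The documents do not support that. Table 2 belongs to the escalation summaries in SAP 5.2.3(a), which name no analysis set, and it is suggested guidance within a review of all the data. The 2/26 example is a boundary case: at 80-90% evaluability a 40-subject arm has 32 to 36 in mITT, and two events do not cross 2% in either set.

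**The lost DVT.** A reader might also infer that confirmed proximal DVTs will be dropped. That goes too far. The Clinical Events Committee charter or the venography manual may deal with positive incomplete films, and neither is available here. No frequency can be given. But mITT membership is an SAP definition, and nothing in the protocol or SAP closes the gap.

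**Limited consequence.** Part 1 tests no hypothesis, the choice of Part 2 doses focuses on any bleeding and total VTE, and MCP-Mod is specified for total VTE only. At apixaban rates of 1-2%, an arm of about 30 expects less than one major VTE (30 × 0.02 = 0.6). A single set also keeps the denominators of the two endpoints equal. These points limit the weight of the finding. They do not justify requiring veins that the endpoint does not use.

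**Conclusion.** The concern holds for SAP 5.2.3(b). The major VTE summaries and odds-ratio intervals rest on a set that demands distal visualisation the endpoint does not need, and on the literal text a diagnosed asymptomatic proximal DVT can fall outside that set.

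The loss is about 9-18% of subjects usable for major VTE at the cited apixaban-arm rates (7-18% over four arms), equivalent to a gain of about 10-22% over mITT in the apixaban arms. Both figures assume that the Table 5 gap reflects proximal-only-evaluable films and that it carries over to this trial. The 10-22% must not be read as the share lost.

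Two stronger statements are not supported: that every deep vein must be seen (three groups are exempt), and that all subjects without a complete film are excluded (symptomatic VTE and death keep a subject in). The Table 2 effect is illustrative only. This is a worthwhile correction to a key secondary endpoint and does not affect the total VTE analysis.

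**What to change.** In SAP 2.4.3.1, add a major-VTE mITT set: all randomized subjects with evaluable proximal veins, or with confirmed proximal DVT, PE or any death. Then:

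- Use it for the major VTE summaries and odds-ratio intervals in 5.2.3(b).
- Name it as the major VTE denominator in 5.2.3(a) and for Table 2 when that table is applied to major VTE, since no set is named there now.
- State that an adjudicated DVT on an incomplete venogram counts as an event and places the subject in the analysis set.

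The cost is SAP wording and one extra adjudication field (proximal veins evaluable, yes or no). The downside is that total and major VTE will have different denominators, as they do in the protocol's own Table 5; a footnote to each table would cover this.

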5.3. Major Secondary Endpoints

- Major VTE
- All individual components of the primary efficacy endpoint
 - Proximal DVT
 - Asymptomatic
 - Symptomatic
 - Distal DVT
 - Asymptomatic
 - Symptomatic
 - Nonfatal PE
 - Any death

5.3.1. Definition

Major VTE is defined as the composite of proximal DVT (asymptomatic confirmed by venography assessment of the operated leg or objectively confirmed symptomatic), nonfatal PE, or any death

→ Major VTE = Proximal DVT (Asymptomatic or Symptomatic) + Nonfatal PE + Any death

The following maps the locations in eCRF of the investigator reported components needed in the definition of Major VTE:

Major VTE Component	eCRF Form name(s)	Comments
Symptomatic DVT (Proximal)	Suspected Symptomatic Deep Vein Thrombosis	In the opinion of the investigator, does this event meet the protocol definition of Symptomatic Deep Vein Thrombosis? → YES & Proximal
Asymptomatic DVT (Proximal)	Planned Day 10-14 Venography	Proximal clot
Nonfatal PE	Suspected Symptomatic Pulmonary Embolism & Death	Suspected symptomatic PE & Alive
Death	Death	

5.3.2. Analysis Methods

See section 5.2.3 above for major VTE summary and analysis.

5.4. Other Efficacy Variable(s)

The following are listed as part of exploratory endpoints in the protocol:

- Other thrombotic events
 - Myocardial Infarction (MI)
 - Ischemic stroke
 - Peripheral arterial embolism

5.4.1. Definition

The following maps the location in eCRF of other efficacy variables

Other Efficacy Variables	eCRF Form name(s)	Comments
Myocardial Infarction (MI)	Suspected Myocardial Infarction/ Unstable Angina	In the opinion of the investigator, does this event meet the protocol definition of Myocardial Infarction → YES
Ischemic stroke	Suspected Stroke / Transient Ischemic Attack (TIA)	In the opinion of the investigator, does this event meet the protocol definition of Stroke → YES

Peripheral arterial embolism	Suspected Peripheral Artery Embolism	In the opinion of the investigator, does this event meet the protocol definition of Peripheral Artery Embolism? → YES
------------------------------	--------------------------------------	---

5.4.2. Analysis Methods

Incidence of Myocardial Infarction (MI), Ischemic stroke and Peripheral arterial embolism up to day 10-14 visit observation period will be summarized by treatment group for the modified ITT (mITT).

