- To assess the effect of JNJ-64179375 compared with apixaban on wound or joint complications in the operated leg

Exploratory Objectives

- To assess the effect of JNJ-64179375 compared with apixaban on other thrombotic events (ie, myocardial infarction [MI], ischemic stroke, peripheral arterial embolism)
- To evaluate the cost effectiveness of JNJ-64179375 compared with apixaban based on health resource utilization
- To assess the PK, PD, and PK/PD relationships of JNJ-64179375 in men and women undergoing primary unilateral TKR surgery and the relation of these measures to efficacy and safety endpoints (eg, exposure-response analyses)
- To evaluate the PD assays (TT, ECT, PT, aPTT, and D-dimer) to determine the most appropriate tests to measure the effect of JNJ-64179375

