11.1. Analysis Datasets

The 2 elements that define an analysis data set are:

- The analysis population, which specifies those subjects who will be included in an analysis
- The observation period, which specifies the time window within which data will be included in an analysis

Efficacy Analyses

Two populations will be used in the efficacy analyses:

- Modified Intent to Treat (ITT): all randomized subjects with an evaluable venography assessment or a confirmed symptomatic VTE event, or any death.
- Efficacy Per Protocol: all randomized subjects with no major protocol deviations (to be defined in the SAP) and an evaluable venography assessment within 24 hours after the last dose of the oral study drug or with confirmed symptomatic VTE within 2 days of the last dose of oral study drug, or any death within 2 days of the last dose of oral study drug. Subjects without symptomatic VTE or death must also have received the single complete infusion of JNJ-64179375 or at least 18 doses of oral apixaban.

The 2 observation periods to be used in the efficacy analyses include the following:

- Up to Day 10-14 visit (venography assessment)
- Up to the Week 18 visit

The primary efficacy endpoint analysis (total VTE) will use the modified ITT population up to the Day 14 observation period. Additional details will be provided in the SAP.

Bleeding Event Analyses

Two populations will be used in the bleeding event analyses:

- Safety: all randomized subjects who received at least 1 dose (partial or complete) of active study drug
- Safety Per Protocol: all randomized subjects with no major protocol deviations who received the single complete infusion of JNJ-64179375 or at least 18 doses of oral apixaban or with a bleeding event centrally adjudicated by the CEC within 2 days of the last dose of oral study drug

The 3 observation periods to be used in the bleeding event analyses include the following:

- Up to Day 10-14 visit (venography assessment)
- Up to the Week 5 visit
- Up to the Week 18 visit

The primary bleeding event analysis (any bleeding) will use the safety population up to the Day 10-14 visit observation period.

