2.4.4. Safety Analysis Set

Safety analysis set includes all randomized subjects who received at least 1 dose (partial or complete) of active study drug

Safety Per Protocol analysis set includes all randomized subjects with no major protocol deviations who received the single complete infusion of JNJ-64179375 or at least 18 doses of oral apixaban or with a bleeding event centrally adjudicated by the Clinical Events Committee (CEC) within 2 days of the last dose of oral study drug

Safety Per Protocol analysis set details: Safety Per Protocol analysis set includes all randomized subjects, in the Up to Day 10-14 visit observation period with:

- No major protocol deviations (see section 4.5 for major protocol deviation)
→ this is expected to come from Data Management
- Subject received the single complete infusion of JNJ-64179375 or at least 18 doses of oral apixaban
→ that is, in the “Study Drug Administration” eCRF form for JNJ-64179375, “Was the Total administered?” should be equal to “Yes” or for apixaban, total # doses ≥ 18 .
- Subject bleeding event centrally adjudicated by the CEC within 2 days of the last dose of oral study drug
→ that is, CEC adjudicated bleeding event date \leq last oral (apixaban) dose date + 2 days

The 3 observation periods to be used in the bleeding event analyses include the following:

- Up to Day 10-14 visit (venography assessment)
- Up to the Week 5 visit
- Up to the Week 18 visit

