6.4. Adverse Events

The verbatim terms used in the CRF by investigators to identify adverse events will be coded using the Medical Dictionary for Regulatory Activities (MedDRA). Any AE occurring at or after the initial administration of study agent through the day of last dose to up to last contact date is considered to be treatment emergent. If the event occurs on the day of the initial administration of study agent, and either event time or time of administration are missing, then the event will be assumed to be treatment emergent. If the event date is recorded as partial or completely missing, then the event will be considered to be treatment emergent unless it is known to be prior to the first administration of study agent based on partial onset date or resolution date. All reported treatment-emergent adverse events will be included in the analysis. For each adverse event, the number and percentage of subjects who experience at least 1 occurrence of the given event will be summarized by treatment group. In addition, comparisons between treatment groups will be provided if appropriate.

Summary tables will be provided for:

- All AEs and TEAEs
- All Serious AEs (SAEs) and TESAEs
- AEs leading to discontinuation of study agent/termination of study participation
- TEAEs by severity
- TEAEs by relationship to study agent

In addition to the summary tables, listings will be provided for subjects who:

- Had SAEs
- Had AEs leading to discontinuation of study agent

Incidence of other treatment-emergent adverse events of special interest will be summarized.

As per protocol, adverse events of special interest include bleeding events, infusion reactions, hypersensitivity reactions, and wound or joint complications. All suspected symptomatic efficacy(thrombotic) events will also be captured as adverse events of special interest. Subjects with adverse events of special interest may be counted or listed using MedDRA SMQs (eg, hemorrhage excluding laboratory terms SMQ).

The following maps the location in eCRF of adverse events of special interest

Adverse events of special interest	eCRF Form names(s)	Comments
Specify AE special interest type	Adverse Events/Serious AEs	

Deaths will be displayed by actual treatment received. Frequencies for the following parameters will be included in the summary table:

- Number of subjects who died
- Cause of death
- Relationship to study agent (yes/no)

A listing of subjects who died will be provided.

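### The endpoint table for MI, ischemic stroke and peripheral arterial embolism is restricted to mITT, so nonfatal events in subjects with no evaluable venogram and no symptomatic VTE are left out of it

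*SAP*

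**What the plan says.** The protocol's exploratory objectives (section 2.1.1) include this one: "To assess the effect of JNJ-64179375 compared with apixaban on other thrombotic events (ie, myocardial infarction [MI], ischemic stroke, peripheral arterial embolism").

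SAP 5.4.2 gives the Part 1 analysis in one sentence. It covers "Incidence of Myocardial Infarction (MI), Ischemic stroke and Peripheral arterial embolism up to day 10-14 visit observation period", which "will be summarized by treatment group for the modified ITT (mITT"). No second analysis set is named for these events.

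SAP 2.4.3.1 defines mITT as "all randomized subjects with an evaluable venography assessment or a confirmed symptomatic VTE event, or any death". An MI, stroke or arterial embolism does not by itself qualify a subject. Protocol 11.1 gives the framework: "Two populations will be used in the efficacy analyses". These are mITT and Efficacy Per Protocol, and the second carries the same kind of venogram, VTE or death condition.

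The set with no imaging condition is in SAP 2.4.4: "Safety analysis set includes all randomized subjects who received at least 1 dose (partial or complete) of active study drug". Adverse events are analyzed on it (note to SAP Table 5). SAP 6.4 adds: "All suspected symptomatic efficacy(thrombotic) events will also be captured as adverse events of special interest".

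**The concern.** Restricting total VTE to mITT makes sense, because asymptomatic DVT cannot be classified without a venogram. The same restriction does not suit arterial events. They need no venogram, and the Time and Events Schedule has symptomatic thrombotic events assessed in all subjects at every visit from Day 1.

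The protocol waives the venogram after PE or symptomatic proximal DVT, and mITT takes those subjects back through its VTE clause. There is no matching clause for arterial events. A subject who survives an MI or stroke early in the dosing phase and does not have an evaluable venogram leaves the table together with the event.

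At stake is whether the endpoint table for a new thrombin-directed antibody against apixaban shows the nonfatal arterial events that occurred. Such events are likely to be few in cohorts of about 40 active subjects, so one or two omissions would visibly change the table.

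**Working it through.** The plan states no figure for this endpoint, so there is nothing to reproduce. The check sets the definitions side by side and then sizes the effect under stated assumptions.

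**Who is counted in SAP 5.4.2 (event before the Day 10-14 visit)**

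| Subject with MI, stroke or arterial embolism | In mITT? | Event in the 5.4.2 table? |
|---|---|---|
| Evaluable venogram obtained | Yes | Yes |
| No evaluable venogram, confirmed symptomatic VTE | Yes | Yes |
| No evaluable venogram, died | Yes | Yes |
| No evaluable venogram, alive, no symptomatic VTE | No | No |

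Only the last row is lost.

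**Size for arterial events**

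Inputs:
- e, evaluability in subjects without an event: 80% to 90%. Protocol 11.2 expects 10% to 20% without an evaluable venogram. It says this of Part 2; applying it to Part 1 is an assumption.
- r, true nonfatal event rate: assumed 2%. The documents give none.
- m, probability that an event subject has no evaluable venogram (and no symptomatic VTE): assumed, varied up to 100%. The documents give none.

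Formula: mITT rate = r(1 − m) / [r(1 − m) + (1 − r)e].

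Example, e = 0.80, m = 0.50: 0.02 × 0.50 = 0.010; 0.98 × 0.80 = 0.784; 0.010 / 0.794 = 1.26%.

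| m | mITT rate, e = 80% | mITT rate, e = 90% | Safety-set rate |
|---|---|---|---|
| equal to 1 − e (20% or 10%) | 2.0% | 2.0% | 2.0% |
| 50% | 1.26% | 1.12% | 2.0% |
| 80% | 0.51% | 0.45% | 2.0% |
| 100% | 0% | 0% | 2.0% |

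With r = 1% or 5%, e = 80% and m = 50%, the mITT rate is 0.63% or 3.18%. There is no bias when event subjects miss the venogram as often as others.

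One-cohort illustration: of 40 dosed active subjects, 80% evaluable gives 32 in mITT. If two nonfatal events both fall among the other 8, the safety set reads 2/40 = 5.0% and mITT reads 0/32 = 0%.

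**Side effect on the VTE components (SAP 5.2.3(b))**

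That section plans: "Incidence of total VTE, major VTE with associated component events up to day 10-14 visit observation period will be summarized by treatment group", on mITT. Here no confirmed symptomatic VTE or death is lost, because each one admits its subject. Event-free subjects without a venogram do leave the denominator. The mITT set holds at least the evaluable fraction of subjects, so the incidence of nonfatal PE, symptomatic DVT or death is overstated by at most 1/0.90 = 1.11 to 1/0.80 = 1.25, that is, up to about 11% to 25%.

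**The case against.** The strongest reply is that these events are not lost to the report. Protocol Time and Events Schedule footnote o lists MI, ischemic stroke and peripheral arterial embolism among the suspected symptomatic thrombotic events, and SAP 6.4 makes those adverse events of special interest and summarizes their treatment-emergent incidence. Adverse events use the safety set, and treatment emergence runs to last contact, past Day 10-14. This stands, and it rules out the reading that the events are counted nowhere else. It is still only a partial safeguard: it covers suspected events reported as adverse events, over a different window, and is not the endpoint incidence that section 5.4 sets out to give.

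A reader might also infer that every arterial event without a venogram is dropped. The definition does not support that: a fatal event, or one accompanied by confirmed symptomatic VTE, stays in mITT.

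A reader might infer that most survivors of an MI or stroke will miss venography. The documents give no such rate. They ask subjects who stop oral drug early to return at the scheduled Day 10-14 visit for the venogram, and SAP Table 1 accepts a venogram on any day. The direction of bias is plausible but not established.

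It would also go too far to say that an adjudicated comparison is corrupted. SAP 5.4.1 maps these events to the investigator's opinion on the eCRF, and 5.4.2 plans an incidence summary with no interval or test. If m and e are alike in both arms, the ratio of two small rates is roughly preserved; the counts and absolute rates are what suffer.

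Finally, SAP 5.4.2 follows protocol 11.1, which names only two efficacy populations. That explains the choice but does not make the set fit an endpoint that needs no venogram.

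**Conclusion.** The point holds for the endpoint summary and for nonfatal events. SAP 5.4.2 conditions the count of arterial events on a set whose membership those events can affect, and no safety-set version of that table is specified. How much is lost cannot be fixed from the documents: under the assumed 2% rate and 80% evaluability, the table would show anything from the true 2.0% down to 0%, according to how often event subjects miss venography.

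The effect on the VTE components is secondary. No event is lost, the overstatement is at most about 11% to 25% at the protocol's own range, and it is similar in both arms if evaluability is similar. A reader might infer a larger figure from protocol Table 5, where the apixaban total-VTE denominators are 1157/1599 = 72.4% and 976/1528 = 63.9% of those for symptomatic VTE. Those are other trials, which included surgery on one or both knees (protocol 1.2), and their evaluability cannot be assumed here.

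Priority is minor. The endpoint is exploratory, Part 1 tests no hypothesis, and no suggested stopping criterion in SAP 3.1.1 uses arterial events.

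**What to change.** In SAP 5.4.2, summarize MI, ischemic stroke and peripheral arterial embolism by treatment group on the safety analysis set. The mITT version may stay as a supplement.

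Optionally, in SAP 5.2.3(b), show nonfatal PE, symptomatic DVT and death on the safety set beside the mITT component breakdown. Keep mITT for endpoints that need the venogram.

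The cost is one additional table (more if the optional display is added) and a note that it uses a set other than the two efficacy populations named in protocol 11.1. The data are already collected for all subjects, and no power or alpha calculation changes.
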